In the MONALEESA-2 study, neutropenia was reported in 74% of patients in the experimental arm, of these 49% had grade 3/4 neutropenia; in the placebo arm only 5% of patients reported neutropenia; anemia was reported in 18% of the ribociclib arm and 4.5% of the placebo arm; most cases were grade 1/2, leukopenia was also reported in the ribociclib arm. Nausea was reported in 51% of patients in the experimental arm and 28% of the placebo arm. Alopecia in 32% and 15% respectively. Transaminitis was also reported in 15% of the patients in the experimental arm and only 3-4% in the placebo arm (mostly grade 1/2). An increase of more than 60 milliseconds from baseline in the QTc interval occurred in 2.7% in the ribociclib group and in no patients in the placebo group (19). Serious AEs occurred in 71 patients (21.3%) in the ribociclib group and in 39 (11.8%) in the placebo group (19). Dose adjustments secondary to an adverse effect were required for 182 (54.5%) of patients treated with ribociclib plus letrozole, which was higher than placebo plus letrozole (14, 4.2%). Median time to first dose reduction was 2.9 (range 0 to 29.4) months. Dose interruptions secondary to an adverse effect were required for 239 (71.6%) of patients treated with ribociclib plus letrozole, which was higher than placebo plus letrozole (54, 16.4%). Neutropenia was the most common reason for dose adjustments and dose interruptions.

In the MONALEESA-3 trial, neutropenia was again the most common reported AE, in the

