ribociclib group 69% of the patients developed neutropenia, 53% grade 3/4 while 2% of patients in the placebo arm developed neutropenia. Other common grade 3/4 AE were nausea (45%), fatigue (31%), leukopenia (28%), vomiting (26%), pruritus (19%), alopecia (18%), anemia (17%). ALT and AST elevation occurred in 4-6% of the ribociclib arm and 1% of the placebo arm. QTc prolongation occurred in 6% of patients in the ribociclib arm; three cases discontinued treatment due to QTc prolongation, there were no cases reported of Torsades de Pointes (21). Serious AE occurred in 138 (28.6%) and 40 patients (16.6%) in the ribociclib plus fulvestrant and placebo plus fulvestrant arms, respectively; of these, 54 (11.2%) and six (2.5%) were attributed to the study medication. The most common all-grade all-causality serious AEs reported in  $\geq 1\%$  of patients (ribociclib plus fulvestrant v placebo plus fulvestrant) were pneumonia (1.9% v 0%) and dyspnea (1.2% v 2.1%) (21). Ribociclib or placebo dose reductions were reported in 183 (37.9%) and 10 patients (4.1%) in the ribociclib plus fulvestrant and placebo plus fulvestrant arms, respectively; 148 (30.6%) and nine (3.7%) had a single dose reduction. AEs were the most common reason for dose reduction (160 of 183 patients with a dose reduction) (21).

Similarly, in the MONALEESA-7 study, 76% of patients in the ribociclib arm developed neutropenia (61% grade 3/4) while 8% of patients in the placebo arm developed neutropenia. Other common AEs were leukopenia (31%), anemia (21%), alopecia (19%), transaminitis (12%). QTc prolongation was reported in 11% of the ribociclib group vs 4% of the placebo arm (23). Dose interruptions or reductions owing to an AE of QTc interval prolongation occurred in 13 (4%) of 335 patients in the ribociclib group and three (1%) of 337 patients in the placebo group. None of the patients with a QTc prolongation event had clinical symptoms or arrhythmias. Overall, dose adjustments occurred in 255 (77%) of patients who received ribociclib compared to 126 (38%) of those who received placebo. Serious AEs occurred in 60 (18%) of 335 patients in the ribociclib group and 39 (12%) of 337 in the placebo group (23).

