# 3 Patient selection

## 3.1 Indication

Women with HR-positive, HER2 negative advanced breast cancer. This phase IV trial will enroll a pre-defined number of patients (n=36) with HR+/HER2- advanced/metastatic breast cancer.

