### **3.2.2 Number of Patients**

Thirty-six patients will be enrolled in total. More specifically, 18 patients will be enrolled into each cohort based on self-identified race.

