## 9.2 Statistical Analysis Plan

Primary analyses will be performed as follows. Within each race-based cohort, the ribociclib exposure which measured by ribociclib AUC will be summarized by median [Interquartile range, IQR], and two-sample t-test if normality holds or Wilcoxon-Mann-Whitney test will be used to compare AUC between CYP3A5 poor metabolizers and CYP3A5 intermediate or normal metabolizer in each independent race-based cohort. Secondary analyses will be performed as follows. Descriptive statistics will be used to characterize the data profile, frequency and percentages for categorical variables, and mean (SD) or median [IQR] for continuous variables based on the data normalization. Multiple regression will be used to identify variables associated with ribociclib AUC. To best account for any factor that may affect ribociclib exposure, covariates to be assessed include CYP3A5 metabolism status, renal function, liver function, age, race, weight, sex, among others. Any covariates with  $P < 0.2$  on univariate analysis will enter the stepwise multiple linear regression model, with  $P < 0.05$  considered statistically significant. This methodology will also be used to assess a change in absolute neutrophil count and QTc as the outcome variable. Depending on data distribution, a two-sample t-test or Wilcoxon-Mann-Whitney test will be used for 1) a change (baseline and C1D8-C1D16) in continuous variables (e.g., QTc, absolute neutrophil count) between CYP3A5 poor metabolizers and CYP3A5 intermediate or normal metabolizers, 2) to check the association between a continuous variables and categorical risk factors. Pearson correlation coefficient or Spearman correlation coefficient will be calculated to measure the association between two continuous variables. Fisher's exact test will be used for checking the association between two categorical variables. AEs will be assessed with descriptive statistics and univariate logistic regression will assess the occurrence of specific AEs with pharmacokinetic properties (e.g., AUC,  $C_{max}$ ). The approach from the linear regressions will be adapted to logistic regression to identify covariates associated with the occurrence of grade III or IV neutropenia.

Descriptive analysis of the PRO-CTCAE adverse event log to determine frequency of adverse events by race and by CYP3A5 genotype.

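### Stepwise selection of covariates for grade III/IV neutropenia tests many candidates at 5% without adjustment: with no real association, about 19–35% of trials would still name one, with a much exaggerated odds ratio

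*Combined protocol and SAP*

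**What the plan says.** Section 9.2 (Statistical Analysis Plan) sets out the covariate search first for ribociclib AUC. The "covariates to be assessed include CYP3A5 metabolism status, renal function, liver function, age, race, weight, sex, among others". Those below P<0.2 "on univariate analysis will enter the stepwise multiple linear regression model", and P<0.05 then counts as significant. The same section extends the method to the toxicity outcome: the "approach from the linear regressions will be adapted to logistic regression to identify covariates associated with the occurrence of grade III or IV neutropenia".

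This text sits among the secondary analyses and is not labelled exploratory. That label is used for the patient-reported-outcome regression later in Section 9.2 and for the gene work in Section 9.3. The q-value and LASSO in Section 9.3 concern the gene list only. For the neutropenia model the plan gives no expected event count, no limit on model size, no penalisation and no multiplicity control.

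Section 3.2.2 fixes the size: "Thirty-six patients will be enrolled in total". Race is itself a candidate covariate, so the model pools both cohorts. Section 3.1 limits the population: "Women with HR-positive, HER2 negative advanced breast cancer". Sex is therefore constant, and six of the seven named covariates are usable.

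**The concern.** A screen at P<0.2 followed by stepwise selection at P<0.05 tests every candidate at about 5%, and nothing limits the chance that at least one passes. A covariate that survives is picked because its estimate happened to be large. Its odds ratio is then biased away from 1 and its p-value is too small.

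Neutropenia is the most common reason for dose change in the background data of Section 1.2.4. Comparing toxicity between the race cohorts is the first secondary objective (Section 2.3), and race and CYP3A5 status are both candidates. A chance finding on either could be read as a racial or genetic risk factor for the drug's main toxicity.

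**Working it through.** The plan states no event count or error rate for this model, so there is no figure to reproduce.

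**Inputs from the documents.** n = 36, 18 per cohort. Six usable named candidates. Phenotype limits per cohort in Section 3.3 (at least 3 of the rarer phenotype, at most 15 of the commoner), taken here as 3/15 and 15/3. Grade 3/4 neutropenia rates from Section 1.2.4: 53% (MONALEESA-3), 61% (MONALEESA-7) and 62% (phase 1b/2, 600 mg). For MONALEESA-2, "neutropenia was reported in 74% of patients in the experimental arm, of these 49% had grade 3/4 neutropenia" can be read as 49% of all patients or as 0.74 × 0.49 = 36%.

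**Assumptions.** Ten candidates stand for the open list. Patients are followed for one cycle (Section 4.3.10) and the documents give no one-cycle rate, so rates of 20–50% are tried as well.

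**Step 1: numbers per candidate.** Events = 36 × rate. Rarer class = min(events, 36 − events).

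| Rate | Events | Rarer class | Per candidate, 6 | Per candidate, 10 |
|---|---|---|---|---|
| 36% | 13.1 | 13.1 | 2.2 | 1.3 |
| 49% | 17.6 | 17.6 | 2.9 | 1.8 |
| 53% | 19.1 | 16.9 | 2.8 | 1.7 |
| 61% | 22.0 | 14.0 | 2.3 | 1.4 |
| 62% | 22.3 | 13.7 | 2.3 | 1.4 |
| 20% (assumed) | 7.2 | 7.2 | 1.2 | 0.7 |
| 30% (assumed) | 10.8 | 10.8 | 1.8 | 1.1 |

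The rarer class is 13–18 at the quoted rates, or about 1–3 per candidate over most of the table.

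**Step 2: chance of at least one false finding.** For k independent tests at 5% it is 1 − 0.95^k: 26.5% for k = 6 and 40.1% for k = 10.

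The planned procedure was simulated with no true association. Race and CYP3A5 status had the layout above and the other covariates were independent normal. The screen was at P<0.2, selection at P<0.05, with 1,000 runs per setting and event rates of 25–50%.

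| | 6 candidates | 10 candidates |
|---|---|---|
| At least one covariate retained | 19–24% | 31–35% |

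Monte Carlo error is about √(0.24 × 0.76/1,000) = 1.4 percentage points. Varying the test (Wald or likelihood ratio), the direction of selection and the event rate (20–61%) widens the ranges to 15–34% and 25–49%.

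**Step 3: what drives it.** Testing the covariates one at a time, with no stepwise step, gave 18–34% over the same settings. The linear AUC model, which has no event-count problem, gave 25% with six candidates and 39% with ten. The number of unadjusted tests therefore accounts for the error rate.

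**Step 4: size of the false effects.** The median odds ratio of a falsely retained covariate, ignoring direction, was 3.3–4.0. The true value was 1.

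**Step 5: separation.** With six covariates, separation occurred in about 3–5% of runs.

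**Step 6: race and CYP3A5.** With poor metabolisers at 3/18 and 15/18, the phi correlation is (15 × 15 − 3 × 3)/(18 × 18) = 216/324 = 0.67. Selection between the two is unstable.

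**Step 7: the replacement.** A three-term Firth model with no selection gave at least one P<0.05 in about 6–8% of null runs with Wald tests, and about 13% with penalised likelihood-ratio tests. The independent-test figure is 1 − 0.95³ = 14.3%.

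**The case against.** The strongest reply is that this is one sentence among secondary analyses. It promises no familywise 5%, and no decision depends on it. Neutropenia is also covered by change in absolute neutrophil count, by univariate logistic regression on pharmacokinetics and by descriptive summaries. The plan says the linear approach will be adapted, which need not mean identical thresholds. With six candidates, 76–81% of null trials would retain nothing. All of this stands and limits the weight of the point. It does not remove it, because the text sets P<0.05 as the mark of significance and does not call the model exploratory.

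Several stronger readings are tempting, and the documents do not support them:

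- A reader might infer that few events per candidate cause the false findings. They do not: the rate with six candidates was no higher at fewer events, and the linear model does no better. Small numbers affect the size of the estimates.
- A reader might infer that the stepwise step itself inflates the error rate. One-at-a-time testing gives nearly the same rate.
- A reader might infer from the 3/15 split that the logistic fit will break down. In the pooled model CYP3A5 status is 18 against 18, and separation is only occasional with six covariates.
- A reader might treat the background rates as a ceiling. They are whole-treatment figures from trials in which 1.9% of ribociclib-treated women were Black (Section 1.3), whereas half of this trial will be. A lower one-cycle rate is plausible but not documented.

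It is also fair to say that the replacement does not bring the familywise error to 5%. For that reason it should carry no significance claims beyond its stated terms.

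**Conclusion.** The point holds as a should-fix on a secondary analysis. With no real association, the planned search would name at least one covariate for grade III/IV neutropenia in about 19–24% of trials with six candidates and 31–35% with ten. Its odds ratio would typically be 3.3–4.0 in one direction or the other, and its p-value would be too small. The primary comparison of AUC between CYP3A5 groups is untouched.

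The figures rest on assumed event rates of 25–50%, ten candidates for the open list, and independence of the covariates other than race and CYP3A5 status. Real correlation among age, weight and renal function would lower the effective number of tests somewhat. A longer list would raise the error rate. The listing of sex is a slip that changes no result.

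**What to change.** Replace stepwise selection for this outcome by one Firth-penalised logistic model with at most three terms, which the sponsor names in the SAP before the data are seen. An example is log AUC, baseline absolute neutrophil count, and either race cohort or CYP3A5 status. Including both of the last two is unwise given their correlation.

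- Report every coefficient with its 95% confidence interval, whatever its p-value, and state which test or interval method is used.
- Label the model exploratory.
- Show any other covariates one at a time as estimates with intervals, with no claim of significance.
- Drop sex from the list as housekeeping.

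The cost is SAP wording only: AUC, neutrophil count and race are already collected. The downside is that there is no data-driven search for further covariates, which 36 women cannot reliably support.

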Hematologic toxicities are seen with CDK 4/6 inhibitors in general, even though neutropenia is common, the incidence of neutropenic fever is low with these treatments (19, 21, 23, 25). There are limited data on the hematologic safety profile of CDK 4/6 inhibitors in African Americans/Blacks. The PALINA study assessed the safety of palbociclib in African American/Black women with and without benign ethnic neutropenia (BEN). A polymorphism in the Duffy antigen has been implicated in the pathophysiology of BEN. A total of 35 African American/Black patients (58% with Duffy null phenotype) with a baseline absolute neutrophil count  $>1000/\mu\text{L}$  were enrolled in this phase 2 study. Women with duffy null phenotype required more dose reductions due to neutropenia; however, this did not result in treatment discontinuation or febrile neutropenia. This study showed that palbociclib is safe in African American/Black women, including those with Duffy null phenotype and baseline absolute neutrophil count 1000-1499/ $\mu\text{L}$  (26).

Transaminitis and QTc prolongation are AEs reported with ribociclib (19, 21, 23, 25). Lung toxicity is a rare but often fatal AE of CDK 4/6 inhibitors, it was reported in one patient in MONALEESA 3, and in several case reports (21).

Based on a dedicated hepatic impairment Study A2109 in healthy subjects with normal hepatic function (N=11) and volunteers with hepatic impairment (N=17), mild (Child-

22

Version 3.6 – 9/28/2023

Pugh class A; N=6) hepatic impairment did not affect the exposure of ribociclib. The mean exposure for ribociclib was increased less than 2-fold in patients with moderate, in 6 patients with Child Pugh class B AUC increased to 1.32 and 5 patients with; Child Pugh class C AUC increased to 1.34. Based on a population pharmacokinetic analysis that included 160 patients with normal hepatic function and 47 patients with mild hepatic impairment, mild hepatic impairment did not affect the exposure of ribociclib, further supporting the findings from the dedicated hepatic impairment study there are no dose reduction recommendations for patients with hepatic impairment (27).

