### 2.3 Secondary Objectives

1. To evaluate toxicity profiles (e.g., QTc prolongation, leukopenia) between each race-based cohort.
2. To characterize ribociclib pharmacokinetics in African American/Black and the Non-Hispanic White patient cohorts.
3. Conduct an exploratory candidate gene analysis of other genes with a biologically plausible role in ribociclib pharmacokinetics or therapeutic response (e.g., *CYP3A4*).

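### Section 9.2 neither names nor forces in baseline ANC for the neutrophil models and leaves the scale of ANC change undefined, so a difference in starting counts could be read as a race effect

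*Combined protocol and SAP*

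**What the plan says.** All the relevant modelling text is in Section 9.2.

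- The covariate list is introduced for exposure: "To best account for any factor that may affect ribociclib exposure", the "covariates to be assessed include CYP3A5 metabolism status, renal function, liver function, age, race, weight, sex, among others". Baseline ANC and Duffy status are not named.
- Selection is data-driven. Covariates with P < 0.2 "on univariate analysis will enter the stepwise multiple linear regression model". Nothing is forced in.
- The list is then reused: "This methodology will also be used to assess a change in absolute neutrophil count and QTc as the outcome variable". Whether change means a difference, a percentage or a log ratio is not said.
- The approach is finally carried over to a binary outcome: it "will be adapted to logistic regression to identify covariates associated with the occurrence of grade III or IV neutropenia".
- Separately, t or Wilcoxon tests by CYP3A5 group are planned for "a change (baseline and C1D8-C1D16) in continuous variables (e.g., QTc, absolute neutrophil count").

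Elsewhere in the protocol:

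- Section 2.3 makes the race comparison of toxicity a secondary objective: "To evaluate toxicity profiles (e.g., QTc prolongation, leukopenia) between each race-based cohort". Section 2.4 lists neutropenia among the secondary endpoints.
- Section 1.2.4 describes benign ethnic neutropenia and its link to the Duffy antigen. It cites a palbociclib study of 35 African American/Black patients, 58% of them Duffy null, and reports: "Women with duffy null phenotype required more dose reductions due to neutropenia".
- Section 3.3 admits patients with ANC of 1,200/mm3 or more. Table 10 puts grade 3 neutropenia at 500 to 1,000/mm3 and grade 4 below 500/mm3.
- Section 2.5 lists the Duffy receptor as an example in an exploratory correlation with toxicity such as change in white cells.

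**The concern.** A covariate list chosen to explain drug exposure need not contain the strongest predictor of a count-based toxicity. For an outcome defined by falling below a fixed count, that predictor is where the patient started. Race is a candidate in the model and baseline ANC is not a named one, so race can stand in for the starting count.

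The protocol gives its own reason to expect a difference in starting counts between cohorts. If there is one, the model may credit race with a difference in drug toxicity that is wholly a difference in baseline. Toxicity by race is a stated objective, so this result would be read and reported.

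The undefined scale of ANC change adds a second problem. If change is analysed as a raw difference, patients with low starting counts have less to lose, and the ANC-change model can mislead in its own way.

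**Working it through.** **No figure to reproduce.** The plan states no power, event rate or expected effect for the neutrophil models; the 80% power in Section 9.1 concerns AUC only.

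**Inputs from the documents.** 18 patients per cohort (3.2.2); entry at ANC ≥ 1,200/mm3 (3.3); grade III/IV below 1,000/mm3 (Table 10); at least 3 and at most 15 patients in the minority and majority CYP3A5 phenotype of each cohort (3.3).

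**Assumptions, not in the documents.** Log-normal baseline ANC with geometric mean 4,000/mm3 in one cohort and 3,200, 2,800 or 2,400 in the other; log SD 0.35. The drug effect is the same in both cohorts: either a 60% proportional fall with residual log SD 0.35, or an additive fall of 2,000/mm3 (SD 600).

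**Step 1: two patients, same 60% fall.** 4,000 × 0.4 = 1,600 (fall 2,400, not grade III). 2,400 × 0.4 = 960 (fall 1,440, grade III).

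**Step 2: grade III/IV rates, proportional fall.** Ignoring truncation at 1,200, follow-up ANC is below 1,000 when baseline × 0.4 × error is below 1,000, so

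P = Φ{[ln(1,000/0.4) − ln(GM)] / √(0.35² + 0.35²)} = Φ{ln(2,500/GM) / 0.495}.

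| GM | z | P(grade III/IV) | odds | OR vs 4,000 |
|---|---|---|---|---|
| 4,000 | −0.950 | 17.1% | 0.2065 | 1 |
| 3,200 | −0.499 | 30.9% | 0.4471 | 2.2 |
| 2,800 | −0.229 | 40.9% | 0.6933 | 3.4 |
| 2,400 | 0.082 | 53.3% | 1.1407 | 5.5 |

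Simulation with the entry floor gives almost the same: 17.0% versus 40.5% at 2,800 (OR 3.3), and about 2.2–5.4 over the range. With log baseline ANC in the model, the race OR at 2,800 is 1.04. With equal baselines the unadjusted OR is 1.01.

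**Step 3: additive fall of 2,000/mm3.** Simulated rates at 2,800 are 55.0% versus 22.2%: OR (0.550/0.450) / (0.222/0.778) ≈ 4.3. Over 3,200 to 2,400 the OR is about 2.5–7.5.

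**Step 4: how often race is nominally significant, 18 versus 18.** Simulated trials; likelihood-ratio test of race at 5%.

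| Drug effect | Without baseline ANC | With log baseline ANC |
|---|---|---|
| Proportional, 60% | about 17–65% | 6–8% |
| Additive, 2,000/mm3 | about 26–87% | 6–8% |

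The low end of each range without baseline ANC is the mild gap (3,200). A repeat of 1,500 trials per scenario gave 7–10% in the adjusted column; the likelihood-ratio test is slightly liberal in 36 patients. Fisher's test is more conservative than the unadjusted likelihood-ratio test: about 23% at 2,800 with a 60% fall.

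**Step 5: ANC change as a raw difference.** Under the proportional model the mean fall is GM × [exp(0.35²/2) − 0.4 × exp(0.35²)] = 0.611 × GM: 2,444 at 4,000; 1,955 at 3,200; 1,711 at 2,800; 1,466 at 2,400. The lower-count cohort looks less affected, and a raw-difference t-test flags race in about 29–88% of trials. Under an additive fall of 2,000 the contrast at 2,800 is only 1,887 versus 1,970. A log-scale model with log baseline flags race in about 5–6% of trials under the proportional fall. Taking a log ratio without the covariate is not enough: under an additive fall of 1,500 the log ratios at 2,800 still differ by −0.475.

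**Step 6: CYP3A5.** With a 3/15 and 15/3 split and the Step 2 simulated rates, poor metabolizers have (3 × 0.405 + 15 × 0.170)/18 = 20.9% and expressors (15 × 0.405 + 3 × 0.170)/18 = 36.6%. The pooled OR is (0.209/0.791) / (0.366/0.634) = 0.46. Within each race the simulated CYP3A5 effect is nil, so with race in the model the OR is 1.

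**The case against.** **Baseline ANC is not excluded.** The covariate list is open-ended, so an analyst may add it. That stands: the defect is absence of pre-specification, not prohibition. But an optional candidate passing a P < 0.2 screen in 36 patients is weak protection.

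**The gap is assumed.** No ANC by race is given, and the 58% Duffy-null figure comes from a palbociclib study concerned with benign ethnic neutropenia. This also stands; the sizes above are conditional. At the mild gap the false-positive rate is about 17–26%, which is still well above 5%.

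**The assumed event rate is low.** Section 1.2.4 quotes 49% to 61% grade 3/4 neutropenia in the pivotal trials, over more than one cycle, against 17% here in the higher-count cohort. A 70% fall at 2,800 versus 4,000 gives 63.2% and 35.5%, averaging 49.4%, and the OR is still 3.1. The conclusion does not depend on the low rate.

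**Incidence is a legitimate target.** More patients below 1,000/mm3 is a real difference in occurrence, and Section 2.3 asks for toxicity profiles by cohort. That is right. Unadjusted incidence answers that question; it does not show that the drug acts differently by race. Both can be reported if labelled.

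**Each term is costly.** At the Step 2 rates, 18 × 0.405 + 18 × 0.170 ≈ 10 events are expected. That stands and limits the form of the fix.

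**Duffy is already planned.** Section 2.5 includes it, but as a separate exploratory correlation, not as an adjustment in the neutropenia model.

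**Conclusion.** The point holds for the grade III/IV model. Section 9.2 leaves out of its specification the one covariate that separates starting count from drug effect, while naming race. Given a real baseline gap, the unadjusted race OR is spurious under both drug-effect models tried: about 2.2–5.4 (proportional) and 2.5–7.5 (additive). These sizes rest on the assumed geometric means, spread and fall; with equal baselines there is no distortion. The analysis is secondary, and the primary within-cohort AUC comparison is untouched.

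Four stronger readings are tempting and are not supported:

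- *That the plan analyses ANC change as a raw difference.* The word absolute belongs to the name of the laboratory test; the scale is simply not stated.
- *That the two neutrophil outcomes will show opposite race effects.* This needs a raw-difference scale, a roughly proportional fall and a sizeable baseline gap. Under an additive fall the change contrast largely disappears and only the threshold model misleads.
- *That CYP3A5 status is generally biased.* The pooled OR of 0.46 arises only when race is out of the model, that is, in the univariate screen or if stepwise selection drops race.
- *That the univariate models of adverse events on AUC are confounded.* No link between baseline ANC and AUC is shown.

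**What to change.** In Section 9.2:

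1. Force log baseline ANC into the multivariable grade III/IV neutropenia model, exempt from the P < 0.2 screen and stepwise removal. Keep that model to very few terms or use a penalised fit.
2. Define the ANC outcome as log(ANC at C1D8–C1D16) with log baseline ANC as a covariate, reported as percent of baseline.
3. Report unadjusted grade III/IV incidence by cohort alongside, labelled as the descriptive toxicity profile.

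The univariate models of adverse events on pharmacokinetic measures can stay as planned.

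The cost is SAP wording. Baseline CBC with differential is already in the study calendar (Table 14), so no new data are needed. The downside is one more parameter in a small logistic model, which is why its other terms should be limited.
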